7.7 Safety

7.7.1 Extent of Exposure

Not applicable.

Statistical Analysis Plan

Sponsor Name: Clear Creek Bio, Inc.
Sponsor Protocol ID: CCB-CRISIS-02

Covance Study ID: 000000207395

7.7.2 Adverse Events

AEs will be collected from the time of first dose of study drug through Day 29. After Day 29, only SAEs which are assessed by the Investigator or designated person to be related to study drug and have an onset within 14 days of study completion (Day 29 or earlier if discontinue prior to Day 29) will be collected/recorded. All AEs recorded on the eCRF will be coded using the MedDRA dictionary Version 23.1 (or a later version if updated during the study).

All AE data will be listed by treatment group. In addition, corresponding listings of study drug-related AEs and SAEs will be produced.

The relationship between an AE and study drug is assessed as definite, probable, possible, unlikely, or unrelated. A study drug-related AE is an AE considered by the investigator as definitely, possibly, or probably related to study drug or with missing relationship to study drug.

An overview table will summarize the number and percentage of subjects with at least one of the following AEs, where subjects with more than one AE in a particular category are counted only once in that category:

- any AE;
- AE by maximum severity grade;
- study drug-related AE;
- AE leading to study drug discontinuation;
- study drug-related AE leading to study drug discontinuation;
- severity grade 3 or higher study drug-related AE;
- SAE;
- study drug-related SAE;
- SAE leading to study drug discontinuation;
- AE leading to death;
- study drug-related AE leading to death.

The number and percentage of subjects reporting each AE will be summarized for each treatment group and overall, by System Organ Class (SOC) (sorted alphabetically) and Preferred Term (PT) (sorted by descending overall total) for the Safety population. The following summaries will be produced:

- AEs, by SOC and PT;
- AEs by PT;
- study drug-related AEs, by SOC and PT;
- study drug-related AEs, by PT;
- AEs by relationship to study drug, by SOC and PT;

Statistical Analysis Plan

Sponsor Name: Clear Creek Bio, Inc.
Sponsor Protocol ID: CCB-CRISIS-02

Covance Study ID: 000000207395

- AEs by severity grade, by SOC and PT;
- study drug-related AEs by severity grade, by SOC and PT;
- AEs leading to discontinuation of study drug, by SOC and PT;
- study drug-related AEs leading to discontinuation of study drug, by SOC and PT;
- severity grade 3 or higher AEs, by SOC and PT;
- severity grade 3 or higher study-drug related AEs, by SOC and PT;
- SAEs, by SOC and PT;
- study drug-related SAEs, by SOC and PT;
- SAEs leading to discontinuation of study drug, by SOC and PT;
- AEs leading to death, by SOC and PT;
- study drug-related AEs leading to death, by SOC and PT.

In the above summaries, subjects with more than one AE within a particular SOC are counted only once for that SOC. Similarly, subjects with more than one AE within a particular PT are counted only once for that PT. For summaries by relationship to study drug, subjects with multiple AEs within a particular SOC or PT will be counted under the strongest relationship within that SOC or PT. For summaries by severity grade, subjects with multiple AEs within a particular SOC or PT will be counted under the maximum severity grade within that SOC or PT.

No statistical comparisons of AEs between treatment groups will be performed.

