	
Investigator or designated person to be related to study drug. Treatment-emergent adverse events will be those with an onset after the date and time of first treatment.
 
Subjects who develop Grade 3 or 4 toxicities or SAEs are to be re-evaluated every 2 days, as feasible, until the toxicity returns to Grade ≤ 2 severity.
 
During assessment for adverse events, investigators and site staff are to elicit from the subject any signs or symptoms of mucositis or thrombocytopenia, e.g.:
 
• Ecchymosis/purpura/petechiae• Epistaxis• Hemoptysis• Hematuria• Gingival bleeding• Prolonged bleeding time from needle sticks, abrasions or lacerations• Hematemesis• Rectal bleeding• Blood in stool• Any other unusual bleeding noted by the subject or caregiver
Stopping Criteria	
Individual Criteria:
 
• Participants who develop a Grade 3 toxicity that is assessed by the investigator to be related to the study drug are to be permanently discontinued from study treatment.• Participants who develop a Grade 4 toxicity, regardless of relatedness to study drug, are to be permanently discontinued from study treatment. 
Study-Level Stopping Criteria:
 
Study enrollment is to be paused if any of the below criteria are met:
 
• If ≥ 3 subjects develop the same related Grade 4 (life-threatening) adverse event or laboratory abnormality;• If ≥ 5 subjects develop the same related Grade 3 or 4 adverse event or laboratory abnormality;• If ≥ 10 subjects develop any related Grade 3 or 4 adverse event or laboratory abnormality. 
All adverse events will be reviewed by the DMC during their reviews. Following assessment by the Data Monitoring Committee (DMC), the DMC will determine whether to stop the study, amend the protocol, or continue the study per protocol.

Statistical Analysis	
A separate, detailed statistical analysis plan (SAP) will be finalized prior to locking the database. All analyses of safety and efficacy for this study will be descriptive in nature and presented by group. Subject demographics and baseline characteristics will be summarized. Subject data listings will also be provided.
 
Summaries for quantitative variables will include the mean, median, quartiles,

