10.8 Safety Monitoring for Hematologic Toxicities

Myelosuppression is a known effect of DHODH inhibition that is associated with prolonged exposure and high doses. To reduce the risk of this effect with brequinar in COVID-19 subjects, the extensive brequinar safety database with over 1,000 patients has been evaluated to select a dose level expected to be safe and well tolerated with regard to hematologic toxicity. In addition to enhancing safety by

selecting a relatively brief 5-day exposure and a low brequinar dose, all subjects in the clinical trial will be under the care of highly qualified medical personnel. Clinically significant out-of-range laboratory results will be reported as adverse events.

In addition to real time assessments by the treating clinical team, the Covance Medical Monitor will assess the available hematology data on a periodic basis to identify any pathologic trends or safety issues. Any apparent increase in the expected rate or severity of hematologic safety events will be discussed with the Principal Investigators and the Sponsor. In addition, the Data Monitoring Committee (DMC) will assess available hematology data on a periodic basis to independently assess any pathologic trends or safety issues. If the rate or severity of hematologic toxicities appears to be above the expected rate or the severity appears worse than that expected, the trial enrollment will be suspended and no further subjects will be treated while a comprehensive data review is conducted. Depending on the outcome of the safety review the study may be stopped, the design adjusted, or the study may continue as designed. Individual and Study stopping rules are provided in [Section 8.4](#).

Safety laboratory results are to be initially assessed in real time by the Principal Investigator or designated person. Any study drug-related clinically significant out-of-range laboratories or study drug-related adverse events will be followed as needed until resolution or stable.

The in-clinic assessments and telemedicine/phone call visits will specifically ask about possible hematologic toxicity including any evidence of the list below. Subjects will be provided with a list of the following events in lay terms and will be instructed to call the research team if any of these events occur.

- Ecchymosis/purpura/petechiae
- Epistaxis
- Hemoptysis
- Hematuria
- Gingival bleeding
- Prolonged bleeding time from needle sticks, abrasions or lacerations
- Hematemesis

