- Rectal bleeding
- Blood in stool
- Any other unusual bleeding noted by the subject or caregiver

Any of these symptoms considered clinically significant will be recorded as an adverse event and must be followed until resolved or stable.

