11 STATISTICAL CONSIDERATIONS

A separate, detailed statistical analysis plan (SAP) will be finalized prior to locking the database. All analyses will be descriptive in nature and presented by group.

Summaries for quantitative variables will include the mean, median, quartiles, standard error, minimum, and maximum. For qualitative variables, the summaries will include the number and percentage of subjects for each outcome, and 95% confidence interval (CI), when appropriate. Any statistical testing will be considered exploratory and descriptive. All computations will be performed using SAS® (Version 9.4 or higher).

Subject disposition, subject demographics and baseline characteristics will be summarized. Subject data listings will also be provided. The following sections will briefly summarize of the planned statistical analyses and analysis sets for the primary and secondary endpoints.

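### No planned AE table counts subjects with any bleeding sign or any oral mucosal event, although the protocol has staff ask for both; one prespecified pooled table with intervals would close the gap

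*SAP*

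**What the plan says.** **What is collected.** Protocol v5.0 section 10.8 says the visits and calls "will specifically ask about possible hematologic toxicity including any evidence of the list below". The list has nine named items (ecchymosis/purpura/petechiae, epistaxis, hemoptysis, hematuria, gingival bleeding, prolonged bleeding, hematemesis, rectal bleeding, blood in stool) and a catch-all, "Any other unusual bleeding noted by the subject or caregiver". The synopsis tells staff to "elicit from the subject any signs or symptoms of mucositis or thrombocytopenia", and section 10 repeats this. Not every positive answer becomes data: "Any of these symptoms considered clinically significant will be recorded as an adverse event".

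**What is tabulated.** SAP 7.7.2 states: "The number and percentage of subjects reporting each AE will be summarized for each treatment group and overall, by System Organ Class (SOC") and preferred term (PT). It then lists 16 summaries, 14 by organ class and PT and two by PT alone. Separately, "An overview table will summarize the number and percentage of subjects with at least one of the following AEs"; its 11 lines cover any AE, severity, relatedness, discontinuation, seriousness and death. The section ends its rules with "No statistical comparisons of AEs between treatment groups will be performed".

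**Intervals.** Protocol section 11 says that for qualitative variables "the summaries will include the number and percentage of subjects for each outcome, and 95% confidence interval (CI), when appropriate". SAP 7.6.4.1 and 7.6.4.2 give exact intervals per arm and an interval for the difference for hospital admission and death. SAP 7.7.2 gives none, including for Grade 3-4 AEs and SAEs, whose frequencies are the secondary safety objective in Protocol 4.2 and SAP 2.1.

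**The concern.** Bleeding and mucosal toxicity were singled out in advance. Protocol 3.6 names thrombocytopenia and mucositis as the main dose-limiting toxicities of the high-dose weekly regimen. Protocol 8.2.1 reports two deaths attributed to hemorrhage in a once-weekly cancer study. Staff therefore question every subject, by telephone on Days 2, 3, 5, 6 and 7 among other contacts.

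The SAP never brings the answers together. A nosebleed, bruising, blood in the urine and bleeding gums are different terms and need not share an organ class. If brequinar raised bleeding in general, each row might show one or two extra subjects and no row would show the total. A reader could then take the absence of a difference in any one term as reassurance. Someone could add up the listings afterwards, but the choice of terms would then be made after unblinding.

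**Working it through.** The plan gives no AE rate, power or detectable difference, so there is no figure of its own to reproduce. The check asks how much is lost by splitting one excess over several rows.

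**Inputs**
- About 50 subjects per arm, 1:1 (Protocol 7.1).
- Ten list items (Protocol 10.8, counted).
- Two-sided 5% level (SAP 7.1), used here only as a common yardstick. The SAP tests no AE and should not start to.
- Subject-level bleeding rates: **assumed**, shown over a range.
- Split: **assumed** equal, with one term per affected subject.
- MedDRA coding of the signs is not in the documents, so the number of rows k is varied.

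**Formulas**
- Pooled power = sum over all a > b with two-sided Fisher p ≤ 0.05 of Bin(a; 50, p1) × Bin(b; 50, p2).
- Row power: the same, with p1/k and p2/k.
- Power for at least one of k rows = 1 − (1 − row power)^k. This treats rows as independent; a multinomial simulation of 200,000 trials per cell differs by at most about 0.01.

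**Results**

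| Brequinar vs placebo | Pooled row | Any of 2 | Any of 3 | Any of 4 | Any of 5 | Any of 10 |
|---|---|---|---|---|---|---|
| 10% vs 2% | 0.19 | 0.05 | 0.013 | 0.005 | 0.002 | 0.0001 |
| 15% vs 3% | 0.40 | 0.17 | 0.07 | 0.03 | 0.014 | 0.0009 |
| 20% vs 5% | 0.51 | 0.29 | 0.16 | 0.08 | 0.04 | 0.004 |
| 25% vs 5% | 0.75 | 0.51 | 0.32 | 0.19 | 0.11 | 0.012 |

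**One case by hand, 20% vs 5% over ten rows.** Each row has 20%/10 = 2% against 5%/10 = 0.5%. The expected counts are 50 × 0.02 = 1.0 and 50 × 0.005 = 0.25 subjects. With no placebo events, a row needs 6/50 on brequinar before p falls below 0.05 (p = 0.027; 5/50 gives 0.056).

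**Without a test.** Take an excess of at least 5 subjects in a row as visible by eye. At 20% vs 5% the chance is 0.83 for the pooled row, 0.40 for any of three rows, 0.16 for any of five and 0.03 for any of ten. At 10% vs 2% the figures are 0.40, 0.06, 0.013 and 0.001. At 6% vs 2% even the pooled row shows it in only 0.10 of trials.

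**Mucosal events.** Protocol 8.2.1 names stomatitis and mucositis apart, which supports about two rows. At 20% vs 5% the loss is from 0.51 to 0.29.

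**What intervals would show**
- 10/50 vs 2/50: difference 16 points, Newcombe 95% CI 3.1 to 29.4.
- 1/50 vs 0/50: difference 2 points, CI −5.3 to 10.5.
- 0/50: exact upper limit 7.1%.
- 2/50: exact 95% CI 0.5% to 13.7%.

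**The case against.** Five points can be made for the plan as it stands.

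1. **The SAP follows the protocol.** Protocol 11.2 itself specifies tabulation by PT and organ class, with severity and relationship, evaluated descriptively. This stands: the SAP does not depart from the protocol. A reader might also infer that the protocol commits to confidence intervals for AEs. It does not, because section 11 limits them to where they are appropriate.

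2. **Thrombocytopenia is measured directly.** SAP 7.7.3 summarizes platelets by arm and visit, with change from baseline and the number abnormal. A reader might infer that the hematologic question has no answer in the planned tables; SAP 7.7.3 shows otherwise. But the post-dose draws are on Days 8 and 15 only, and platelet counts do not count clinical bleeding.

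3. **Rows are not all single terms.** Organ-class rows count each subject once, and full listings exist. This stands in part. The three- to five-row columns allow for partial pooling, and the loss remains clear. Organ-class rows also mix in events that are not bleeding.

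4. **The rates are assumed and may be high.** At or below 100 mg daily for five days, Protocol 3.5.2 reports 0/39 with mucositis and 1/39 with mild thrombocytopenia, and only clinically significant signs are recorded as AEs. This stands. At low rates the pooled row would show little too, which is a reason to print its interval.

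5. **The SAP predates the current protocol** (04 November against 19 November 2020). This does not explain the gap, since version 4.0 of 01 October has the same ten-item list.

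**Conclusion.** The omission is real, and repairing it is an inexpensive improvement. No planned table counts subjects with any bleeding sign or any oral mucosal event, and the named secondary safety outcome has no interval.

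For bleeding, splitting cuts power from 0.19-0.75 to 0.0001-0.012 in the ten-row extreme. With three to five rows at 20% vs 5%, it falls from 0.51 to 0.16-0.04. These figures rest on assumed rates, equal non-overlapping splits and 50 per arm. The direction holds at every rate pair and number of rows tried; the size does not carry over to other rates.

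A reader might infer that a mucositis excess would vanish in the same way. The documents support a split over only about two terms, so that loss is smaller. Nor would a pooled row settle the question: in this proof-of-concept trial it is itself only weakly to moderately powered.

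**What to change.** Add one descriptive table to SAP 7.7.2, for the Safety Analysis Set, counting each subject once in each row:

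- **Any bleeding**: a PT list fixed before unblinding, covering the nine named signs plus other hemorrhage terms. The tenth item is open-ended and cannot be a fixed term by itself.
- **Any oral mucosal event**: mucositis, stomatitis, mouth ulcer.

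For each row show n (%), an exact 95% CI per arm and a score-type 95% CI (for example Newcombe) for the risk difference. Give the same intervals for subjects with any Grade 3-4 AE and with any SAE.

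Replace the sentence "No statistical comparisons of AEs between treatment groups will be performed" with: *Intervals are descriptive; no p-values for AEs will be presented.* Leave the PT and organ-class tabulation sentence unchanged. No separate cytopenia row is needed, since SAP 7.7.3 summarizes the blood counts.

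Cost: one term list to agree before unblinding and one extra table, with no new data or visits. The intervals will be wide and should be read that way.

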7.7.3 Laboratory Evaluations

Data for the following hematology and chemistry received from central laboratory will be listed and summarized by treatment group and visit. If data for any additional analytes are also recorded, then these will be listed only.

Statistical Analysis Plan

Sponsor Name: Clear Creek Bio, Inc.
Sponsor Protocol ID: CCB-CRISIS-02

Covance Study ID: 000000207395

Hematology	Chemistry
Hemoglobin	Albumin
Hematocrit	Alkaline Phosphatase
Platelets	Alanine Amino Transferase
Neutrophils Absolute	Aspartate Amino Transferase
Lymphocytes Absolute	Total Bilirubin
Monocytes Absolute	Calcium
Eosinophils Absolute	Chloride
Basophils Absolute	Creatinine
Neutrophils %	Glucose
Lymphocytes %	Potassium
Monocytes %	Sodium
Eosinophils %	Total Protein
Basophils %	Lactate Dehydrogenase
White Blood Cell Count	Blood Urea Nitrogen
Red Blood Cell Count (RBC)	Carbon Dioxide/Bicarbonate
RBC Morphology and Mean Corpuscular Volume	C-Reactive Protein

All laboratory data will be reported in International System of Units (SI) units. Out-of-reference-range values will be flagged as high (H) or low (L) in the listings for all laboratory parameters except C-reactive protein.

For analysis purposes, values preceded by a "<" or a ">" sign (i.e. those below or above the limits of quantification) will be considered equal to the lower or upper limit of quantification, respectively.

Laboratory data will be summarized by visit using standard descriptive statistics for the Safety population. Changes from baseline will also be summarized.

For hematology and chemistry parameters, number and percentage of subjects with abnormal results (not clinically significant, clinically significant) at each visit will be provided for each treatment group.

For each laboratory analyte, the baseline value is defined as last scheduled or unscheduled value collected prior to the first dose of study drug. Assessments carried out on day of first study drug administration are considered to have taken place before the study drug administration, if the corresponding times have not been recorded. For post-baseline, only data from scheduled visits will be included in the summary tables.

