7.3 Exclusion Criteria

1. Any physical examination findings and/or history of any illness that, in the opinion of the study investigator, might confound the results of the study or pose an additional risk to the patient
2. Nursing women or women of childbearing potential (WOCBP) with a positive pregnancy test
3. Treatment with another DHODH inhibitor (e.g., leflunomide, teriflunomide) or other agents known to cause bone marrow suppression leading to thrombocytopenia

4. Platelets $\leq 150,000$ cell/mm 3
5. Hemoglobin < 10 gm/dL
6. Absolute neutrophil count < 1500 cells/mm 3
7. Renal dysfunction, i.e., creatinine clearance < 30 mL/min
8. AST or ALT $> 2 \times$ ULN, or total bilirubin $>$ ULN. Gilbert's Syndrome is allowed.
9. Bleeding disorders or blood loss requiring transfusion in the six weeks preceding enrollment
10. Ongoing gastrointestinal ulcer, or gastrointestinal bleeding within 6 weeks of first dose.
11. Chronic hepatitis B infection, active hepatitis C infection, active liver disease and/or cirrhosis per subject report.
12. Heart failure, current uncontrolled cardiovascular disease, including unstable angina, uncontrolled arrhythmias, major adverse cardiac event within 6 months (e.g. stroke, myocardial infarction, hospitalization due to heart failure, or revascularization procedure).

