10 ADVERSE EVENT REPORTING

An adverse event is any untoward medical occurrence in a patient or clinical trial subject administered a medicinal product and which does not necessarily have a causal relationship with this treatment. An AE can therefore be any unfavorable and unintended sign (including an abnormal laboratory finding), symptom, or disease temporally associated with the use of the medicinal product, whether or not considered related to the medicinal product.

Events that occur prior to first dose will be entered as medical history; events that occur after first dose will be entered as adverse events (AEs) on the AE form.

Subjects will be questioned and observed for evidence of AEs, whether or not judged by the Investigator or designated person to be related to study drug. All AEs will be documented in the subject's medical record and CRF. For any pre-existing condition or abnormal laboratory finding that changes in severity after dosing, this change should be recorded as an AE. New abnormal laboratory findings that are clinically significant are considered AEs. Investigators and site staff are to elicit from the subject and note any signs or symptoms of mucositis and thrombocytopenia (see Section 10.8).

Adverse events will be collected from the time of first dose through Day 29. After Day 29, collect/record only Serious Adverse Events (SAEs) which are assessed by the Investigator or designated person to be related to study drug and have an onset within 14 days of study completion (Day 29 or earlier if discontinue prior to Day 29). AE details are to be documented including start and stop date and times, whether continuous or intermittent, severity, any intervention utilized to correct the event (e.g., medication, surgery, or other therapy), outcome and the relationship to the study drug.

AEs identified in the protocol as critical to the evaluation of safety must be reported to the Sponsor by the Investigator according to the reporting requirements within the time periods specified in the protocol.

AEs determined by the Investigator to be related to study drug must be followed until resolution or until they are considered stable or for at least 30 days after discontinuation of study drug.

Abnormal laboratory values or test results occurring after study enrollment constitute AEs only if they induce clinical signs or symptoms, are considered clinically significant, are Grades 3 or 4, or require therapy.

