7.4 Demographics and Other Baseline Characteristics

Demographics will be listed and summarized by treatment group and overall for the ITT population. Standard descriptive statistics will be presented for the continuous variables of:

- age (years) [calculated as (year of informed consent – year of birth) if age is not recorded on the eCRF];
- weight (kg);
- height (cm);
- body mass index (kg/m²) [calculated as (weight/height²) where weight is in kg and height is in m].

Statistical Analysis Plan

Sponsor Name: Clear Creek Bio, Inc.
Sponsor Protocol ID: CCB-CRISIS-02

Covance Study ID: 000000207395

The total counts and percentages of subjects will be presented for the categorical variables of:

- age group (years) (grouped as <65, \geq 65);
- gender;
- race;
- ethnicity.

In addition, baseline characteristics collected prior to the first dose of study drug will be listed and summarized by treatment group and overall for the ITT population. Standard descriptive statistics will be presented for the continuous variables of:

- temperature ($^{\circ}$ C);
- oxygen saturation, SpO₂ (%);
- respiratory rate (breaths/min).

The total counts and percentages of subjects will be presented for the categorical variables of:

- SARS-CoV-2 viral load (detectable, undetectable);
- COVID-19 symptom type;
- WHO Ordinal Scale.

No formal tests of statistical significance will be performed on the demographic and baseline data.

Other baseline measurements, such as vital signs, laboratory results will be summarized by treatment group with the post-baseline measurements.

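### The only categorical laboratory table ignores baseline status, so new low-grade changes in loosely screened analytes are hard to see; a shift table and a new-or-worsened count should be added

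*SAP*

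**What the plan says.** SAP 7.7.3 plans three kinds of laboratory output for the Safety population.

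- **Continuous summaries by visit.** "Changes from baseline will also be summarized". SAP 7.1 gives the statistics as N, mean, SD, median and range.
- **One categorical summary.** The "number and percentage of subjects with abnormal results (not clinically significant, clinically significant) at each visit will be provided for each treatment group". Nothing in this sentence refers to the baseline value.
- **Listings.** "Out-of-reference-range values will be flagged as high (H) or low (L) in the listings for all laboratory parameters except C-reactive protein". Direction of abnormality is therefore shown in listings and is not specified for the table.

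Baseline is defined: "For each laboratory analyte, the baseline value is defined as last scheduled or unscheduled value collected prior to the first dose of study drug". Baseline results are shown alongside later ones: "Other baseline measurements, such as vital signs, laboratory results will be summarized by treatment group with the post-baseline measurements" (SAP 7.4). After baseline, "For post-baseline, only data from scheduled visits will be included in the summary tables"; on the Schedule of Events those laboratory visits are Days 8 and 15. The SAP names no shift table, no treatment-emergent laboratory count and no table of laboratory values by toxicity grade.

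Protocol section 10 frames a laboratory event as a change from the earlier state: "For any pre-existing condition or abnormal laboratory finding that changes in severity after dosing, this change should be recorded as an AE".

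**The concern.** A subject whose ALT was above normal before dosing and is unchanged on Day 8 is counted exactly like a subject whose ALT became abnormal on study drug. Showing the baseline percentage beside the Day 8 percentage does not separate the two, because two marginal percentages do not show who moved. Mean changes do not count subjects who crossed a limit.

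Entry leaves room for baseline abnormality. The hemoglobin exclusion is "Hemoglobin < 10 gm/dL", so milder anemia can enter. AST and ALT may be up to 2 x ULN. Creatinine is limited only through a clearance below 30 mL/min. Glucose, lymphocytes, LDH and CRP have no limit. Some of these matter for this drug: protocol 8.2.1 reports, among 39 subjects dosed at or below 100 mg daily for five days, one with drug-related severe hyperglycemia and two with drug-related elevated creatinine. It also lists anemia and leukopenia among common brequinar events.

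Laboratory assessments are part of a secondary endpoint (protocol 6.2), and the trial is meant to inform the safety design of later studies. With about 50 subjects per arm there is little precision to spare.

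**Working it through.** The documents state no rate, power or effect size for laboratory abnormalities, so there is no planned figure to reproduce. What follows is an illustration.

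**Inputs**
- n = 50 per arm (protocol 7.1, approximate).
- b = share abnormal at baseline, the same in both arms: 0% to 30%. Assumed.
- Persistence of baseline abnormality to the visit: 100%. Assumed.
- q = new abnormality among baseline-normal subjects: 12% brequinar, 2% placebo. Assumed.

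**Formulas**
- Planned count: p = b + (1 − b)q.
- New-abnormality count, all subjects as denominator: p = (1 − b)q.
- SE of the difference = √{[p₁(1 − p₁) + p₀(1 − p₀)]/50}.

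**Worked case, b = 20%**
- Planned: 0.20 + 0.80 × 0.12 = 29.6% vs 0.20 + 0.80 × 0.02 = 21.6%. Difference 8.0 points. SE = √[(0.2084 + 0.1693)/50] = 8.69 points. Ratio 0.92.
- New only: 9.6% vs 1.6%. Difference 8.0 points. SE = √[(0.0868 + 0.0157)/50] = 4.53 points. Ratio 1.77.

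The difference is the same in both counts. The standard error and the risk ratio are not.

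| b | Planned count | Risk ratio | Diff/SE | New abnormality only | Risk ratio | Diff/SE |
|---|---|---|---|---|---|---|
| 0% | 12.0% vs 2.0% | 6.0 | 2.00 | 12.0% vs 2.0% | 6.0 | 2.00 |
| 5% | 16.4% vs 6.9% | 2.4 | 1.50 | 11.4% vs 1.9% | 6.0 | 1.94 |
| 10% | 20.8% vs 11.8% | 1.8 | 1.23 | 10.8% vs 1.8% | 6.0 | 1.88 |
| 20% | 29.6% vs 21.6% | 1.4 | 0.92 | 9.6% vs 1.6% | 6.0 | 1.77 |
| 30% | 38.4% vs 31.4% | 1.2 | 0.74 | 8.4% vs 1.4% | 6.0 | 1.64 |

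If only baseline-normal subjects form the denominator of the new-abnormality count, its diff/SE is 1.95, 1.90, 1.79 and 1.67 at b = 5%, 10%, 20% and 30%, so the choice of denominator matters little.

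The probability that brequinar shows no excess over placebo, from the two binomial distributions with all 50 per arm, is 2.9% for both counts at b = 0%. At b = 20% it is 21% (planned) against 5% (new only), and at b = 30% it is 26% against 7%.

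**Other assumed rates.** With new abnormality 20% vs 5%, the true risk ratio is 4.0. The planned count shows 1.93 at b = 10% and 1.31 at b = 30% with full persistence, and 2.42 and 1.57 with 50% persistence. Lower persistence softens the attenuation but does not remove it.

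**The case against.** **The toxicities of most concern are protected.** Myelosuppression, in particular thrombocytopenia, is the named risk. Protocol 7.3 excludes platelets at or below 150,000, neutrophils below 1500 and bilirubin above ULN (Gilbert's syndrome allowed). For these, b should be near zero and the two counts nearly coincide. This stands, and it limits the point to other analytes. Some residual baseline abnormality is possible through change between Screening and Day 1, or a central reference limit that differs from the entry limit.

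**The AE tables already cover the serious cases.** AEs are collected from first dose. Under protocol section 10, laboratory findings that are clinically significant, Grade 3 or 4, symptomatic or treated become AEs, and SAP 7.7.2 tabulates AEs by grade and relationship. This also stands. What it leaves out is Grade 1-2 change judged not clinically significant. Worsening of a pre-existing abnormality is less clear: one sentence asks for any change in severity to be recorded as an AE, while a later one confines laboratory AEs to the four conditions above. New low-grade change in a baseline-normal subject has no other categorical summary.

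**The listings show who moved.** With about 100 subjects, individual shifts can be traced by hand. That is possible, but it is not a comparison between arms.

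**Nothing is tested.** The protocol calls all analyses descriptive and SAP 7.7.3 specifies no laboratory test. Difference/SE is used above only to measure how visible an effect would be.

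A reader might infer that every abnormal value is counted. In fact the table counts subjects, at scheduled visits only after baseline. A reader might also infer that the table removes or hides harm in brequinar's favour. Randomization balances pre-existing abnormality in expectation and, with equal persistence, the difference over all subjects is unchanged.

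**Conclusion.** The point holds in a limited form. SAP 7.7.3 has no categorical laboratory output that uses the baseline it defines. For analytes with a loose entry limit or none, this costs precision and attenuates the between-arm ratio. It is not a bias towards brequinar, and it does not materially affect platelets, neutrophils or bilirubin.

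Under the assumed rates the loss is nil at 0% baseline abnormality, about a quarter of the difference/SE at 5% (1.50 against 1.94) and about half or slightly more at 20-30%. Every baseline, persistence and new-onset rate is an assumption; the documents give none. The practical gap is new or worsened Grade 1-2 change judged not clinically significant.

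It would also go too far to say that a baseline-conditioned table would strip out COVID-19 effects. Abnormalities from the infection that begin after the first dose would still count as new, and only the placebo comparison addresses them. The primary viral load analysis is not affected. This is a reporting gap that should be closed because closing it is cheap.

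**What to change.** In SAP 7.7.3, keep the by-visit abnormality table and add two outputs per analyte and direction (low, high):

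1. A baseline-by-visit shift table by DAIDS grade, which is the protocol's own severity scale, using normal/low/high where no grade exists.
2. The number and percentage of subjects with a new or worsened grade (or abnormality, where there is no grade) relative to the baseline already defined, among subjects with both a baseline and a post-baseline value.

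Using grade matters. A count based only on moves from normal to abnormal, or from not clinically significant to clinically significant, would miss a subject whose ALT rises from 1.5 to 4 x ULN with both values judged not clinically significant.

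The cost is SAP wording, a few extra tables and slightly smaller denominators. The values are already collected.
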